9.2.1 Adverse Event

An adverse event (AE) is any untoward medical occurrence in a subject, or clinical investigation subject, administered a pharmaceutical product which does not necessarily have to have a causal relationship with this treatment. An AE can therefore be any unfavorable and unintended sign (including an abnormal laboratory finding, for example), symptom, or increase in severity or frequency of a pre-existing abnormality, temporally associated with the use of a medicinal (investigational) product, whether or not considered related to the medicinal (investigational) product.

9.2.2 Suspected Adverse Reaction

A suspected adverse reaction is any adverse event for which there is reasonable possibility that the drug caused the adverse event. Suspected adverse reactions will consist of the adverse events that are evaluated by the investigator as possibly related or probably related to the study drug and/or study device.

9.2.3 Serious Adverse Event

A serious adverse event (SAE) is any adverse experience occurring after randomization at any dose that results in any of the following outcomes:

- Death
- Is life-threatening (at the time of the event)
- Requires inpatient hospitalization or prolongation of existing hospitalization

- Results in a persistent or significant incapacity or substantial disruption of the ability to conduct normal life functions
- Is a congenital anomaly/birth defect (in an offspring)

Important medical events that may not result in death, be life-threatening, or require hospitalization may be considered an SAE when, based upon appropriate medical judgment, the event may jeopardize the subject and/or the subject may require medical or surgical intervention to prevent one of the outcomes listed in this definition.

9.2.3.1 Hospitalizations as Serious Adverse Events

All AEs requiring hospitalization or prolongation of hospitalization should be reported as SAEs.

Hospitalizations meeting the following criteria will not be reported as an SAE but must be recorded on the appropriate CRF: short-term administrative hospitalization for procedures, tests or treatments of conditions that would not otherwise constitute an SAE, or elective hospitalizations.

9.2.4 Unanticipated Adverse Device Effect

A serious adverse effect on health or safety or any life-threatening problem or death caused by, or associated with, a device, if that effect, problem, or death was not previously identified in nature, severity, or degree of incidence in the investigational plan or application (including a supplementary plan or application), or any other unanticipated serious problem associated with a device that relates to the rights, safety, or welfare of subjects.

9.3 Reporting of Safety Information

9.3.1 Adverse Event Reporting

All AEs, regardless of causality, severity, whether expected or not, must be entered on the AE CRF. Disease-related signs and symptoms that are present at baseline should not be reported as AEs unless they worsen in severity or frequency. Information collected concerning AEs will include the following:

- Name of the event
- Start date
- Stop date or if the event is continuing
- Intensity

- Mild (does not interfere with subject's usual function)
- Moderate (interferes to some extent with the subject's usual function)
- Severe (interferes significantly with subject's usual function)
- Relationship to investigational product (drug, device or both)
- Seriousness of event
- Outcome
- Action taken

Non-serious adverse events will be collected beginning after the first dose of study medication through the End of Study Visit and will include any change from the subject's condition at Screening. All NSAE that are deemed related to study drug and/or study device will be followed until resolution or stabilization of the event. SAEs will be collected following enrollment and will include any change from the subject's baseline condition at Screening. SAE collection will conclude at End of Study or until resolution of the SAE if it extends beyond the End of Study Visit.

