5.2 Study Treatment

5.2.1 Dose Description

This is an open-label study so all eligible subjects will receive a nasal CO₂ hand-held dispenser. One dose will consist of a 10 second administration of nasal CO₂ to each nostril. Subjects will be instructed to use the nasal CO₂ dispenser, 10 sec/nostril, as needed up to 6 times to treat one attack. Each dose must be separated by 3-5 minutes. Subjects should treat only one attack during a 24-hour period with the investigational product. Subjects may treat up to three cluster headache attacks during the treatment phase of this study.

Subjects may receive up to a total of 1.0 L of CO₂ if they treat one attack with 6 doses. Subjects may receive a total of 3.0 L of CO₂ if they treat three headache attacks with 6 doses of CO₂ during this study.

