5.3 Duration

Once enrolled, each subject's participation in the trial may last up to 84 days (12 weeks) or once the subject treats up to 3 cluster headache attacks with the nasal CO₂ dispenser, whichever occurs first. There will be two scheduled clinic visits, Screening and End of Study Visit. The subject may return to the clinic 4 weeks and 8 weeks after the screening visit as necessary for a replacement dispenser. The End of Study Visit should occur within 7 days after the subject treats his/her last cluster headache attack or within 7 days after the completion of the 84-day treatment period, whichever occurs first. If a subject has not treated any cluster headaches during the 12 weeks treatment phase they can be allowed to continue in the study for an additional 12 weeks at the discretion of the Investigator.

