8.2 Schedule of Events

Study Procedures	Screening	Treatment	End of Study Visit ¹
Informed Consent	X		
Eligibility	X		
Medical History/ Medications / Demographics	X		
Physical Examination including Neurological and Nasal Mucosal Exam	X		X
Vital Signs	X		X
Urine Pregnancy Test	X		X
Subject Training	X		
Subject eDiary, AE/ConMed diary, and Questionnaire Instruction	X		
Investigational Product Dispensation	X	X ²	
Accountability of Investigational Product Study Drug and Study Supplies	X		X
Diary Completion		X	
Adverse Event Assessment		X	X
Concomitant Medications Assessment	X	X	X
Telephone Contact		X ³	X
Source Document and eCRF Completion	X		X

¹ The End of Study Visit should occur within 7 days after the subject treats up to his/her third headache or within 7 days after the completion of the 84-day treatment period, whichever occurs first.

² Subjects will return to the clinic at 4 and 8 weeks after the Screening Visit as necessary for a replacement dispenser.

³ Subjects will be contacted by telephone within 3 days of treating their 1st attack to answer any questions, assess if there are any problems with compliance or any concerning AEs.

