10.8.1 Adverse Events

Adverse events (AEs) will be monitored throughout the study. All reported AEs will be documented on the appropriate eCRF. All similar AEs will be combined into one category and the frequency of all AEs occurring above 5% will be reported.

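### Adverse events are reported as crude frequencies over follow-up that runs from a few days to 91 days, so non-specific events cannot be separated from background

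*Combined protocol and SAP*

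**What the plan says.** Section 9.3.1 fixes the collection period: "Non-serious adverse events will be collected beginning after the first dose of study medication through the End of Study Visit". Serious events are collected from enrolment. Every event is entered whatever its cause, with start date, stop date, intensity and relationship to drug or device. Section 8.1.10 has the subject record the time of each dose.

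The end of the period varies. The Schedule of Events (8.2, footnote 1) says "The End of Study Visit should occur within 7 days after the subject treats up to his/her third headache". Section 5.3 says "The End of Study Visit should occur within 7 days after the subject treats his/her last cluster headache attack". Both have an outer limit, which 5.3 words as "within 7 days after the completion of the 84-day treatment period, whichever occurs first". Section 5.2.1 sets the pace of treatment: "Subjects should treat only one attack during a 24-hour period with the investigational product" and "Subjects may treat up to three cluster headache attacks during the treatment phase of this study".

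The AE analysis in 10.8.1 is one rule: "All similar AEs will be combined into one category and the frequency of all AEs occurring above 5% will be reported". Section 10.1 promises 95% confidence intervals with all analyses. Section 10.4.4 limits the safety set to subjects who received the product, but 10.8 runs the safety analyses on all enrolled subjects.

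**The concern.** Safety is half of the primary objective (4.1), and nothing in a single-arm trial shows how often these events occur without CO₂. The treatment is brief and intermittent. In the migraine study C113 (3.3.4.5), events typically stopped when administration stopped. Most of a long follow-up window is therefore time without exposure, yet an event on day 60 counts the same as one during dosing.

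Section 3.4 lists headache, nausea, dizziness and upper respiratory tract infection among the anticipated events, and all of these can occur without the product. A crude frequency for such a category rises with follow-up, and follow-up differs between subjects for reasons unrelated to the safety of the gas. If 10.8 is followed literally, a serious event before any dose enters the frequency too, and subjects with no non-serious AE window at all enter the denominator.

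**Working it through.** The plan states no window length, expected AE rate or sample-size calculation, so there is no figure of its own to reproduce.

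**1. Length of the non-serious AE window** (9.3.1, 5.2.1, 5.3, 8.2). The first dose is taken to be the first one used on an attack.
- Fastest three-attack subject: attacks on days 0, 1 and 2, with the visit between day 2 and day 2 + 7 = 9. Nine days is the latest close for this subject, not a minimum.
- One treated attack under 5.3: the visit falls 0 to 7 days later.
- Longest: first dose on day 0, visit on day 84 + 7 = 91.
- Ratio of 91 to 9 days: 91/9 = 10.1.
- The discretionary 12-week extension in 5.3 applies only if no attack was treated, so it does not lengthen this window beyond about 91 days. The serious-event window, which starts at enrolment, can reach 84 + 84 + 7 = 175 days.

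**2. Exposure** (5.2.1). 3 attacks × 6 doses × 20 seconds = 360 seconds, or 6 minutes at most.

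**3. Background, any AE.** The rate is an assumption: 0.5 to 4 events per person-year, constant, with no CO₂ effect. P(at least one event) = 1 − exp(−rate × days/365.25).

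| Rate per year | 9 days | 91 days |
|---|---|---|
| 0.5 | 1.2% | 11.7% |
| 1 | 2.4% | 22.1% |
| 2 | 4.8% | 39.2% |
| 4 | 9.4% | 63.1% |

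**4. One category against the 5% reporting line.** With 25 subjects, 1/25 = 4% and 2/25 = 8%, so a category needs two subjects to be reported. Assume a background of 0.02 per month for the category.
- Per-subject probability: 1 − exp(−0.02 × 9/30.44) = 0.59% over 9 days, and 1 − exp(−0.02 × 91/30.44) = 5.8% over 91 days.
- P(two or more of 25) = 1 − (1 − p)^25 − 25p(1 − p)^24. This is about 1% if everyone has 9 days and about 43% if everyone has 91 days.
- If half the subjects have each window (an illustration, not a forecast), the mean is (0.59 + 5.8)/2 = 3.2%, or 25 × 0.032 = 0.8 subjects expected. That is below the line.

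**5. The one controlled comparison of AE rates in the documents** (C113, 3.3.4.5). Nasal discomfort was 36.8% on CO₂ and 12.5% on placebo. The excess is 36.8 − 12.5 = 24.3 points, and 24.3/36.8 = 66% of the CO₂ frequency.

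**The case against.** Four arguments carry weight.

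- **A reader might infer that the reported frequencies will reflect follow-up time and background illness more than CO₂.** The documents do not support that. It would need a background rate and a follow-up distribution, and neither is given. For the main expected event the C113 figures point the other way.
- **Long windows may be uncommon.** Section 3.2 describes attacks occurring from several times a day to several times a week. Three could be treated within about a week of the first dose, giving 7 + 7 = 14 days of follow-up. The 12-hour medication rule in 7.2.2 may delay some subjects. At 1 event per year, 14 days gives 1 − exp(−14/365.25) = 3.8%, far from 22.1%.
- **A reader might also infer that the least exposed subjects are followed longest.** This holds only under footnote 1 of 8.2, where a subject who stops after one attack can wait for the outer limit. The synopsis, 5.0 and 5.3 tie the visit to the last treated attack, which gives that subject a short window. Unequal windows remain under either rule, because attacks can be spread over the period.
- **The data needed are already collected.** Onset dates, dose times and relatedness are recorded, 9.2.2 defines suspected adverse reactions, and 9.3.1 leaves out baseline disease symptoms unless they worsen. Nothing is lost if the tables are added later. This limits the gap to the analysis plan, but 10.8.1 uses none of these fields, and relatedness is judged open-label.

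A further caution concerns the remedy. If only events on the dosing day or the next day entered the main table, nasal mucosal changes found at the End of Study examination (8.1.5, 10.3.5) would usually drop out of it.

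**Conclusion.** The point holds as a gap in the analysis plan, not in data collection. Non-serious AE follow-up varies from a few days to 91 days, serious events count from enrolment, and 10.8.1 makes no allowance for either. Frequencies of non-specific events will therefore mix background with CO₂ effect in a proportion the trial cannot show.

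The size is conditional. Between a 9-day and a 91-day window, the chance of at least one background event changes roughly 7- to 10-fold over the assumed rates (63.1/9.4 = 6.7; 11.7/1.2 = 9.8). How much of that reaches the reported frequencies depends on the actual spread of follow-up. Administration-site events are less affected. The change is worth making because it bears on a primary objective and costs little.

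**What to change.** Amend 10.8.1 as follows.

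1. Keep a main table of all AEs starting after the first dose, in dosed subjects, and show days of follow-up. Use the 10.4.4 set and reconcile 10.8 with it.
2. Within that table, report separately, with the 95% confidence intervals promised in 10.1: events starting on the day of a CO₂ dose or the next day; later events; and events judged related to drug or device.
3. List serious events before the first dose separately.
4. Keep nasal mucosal findings from the End of Study examination in the main table whatever their onset date.
5. State whether the brief training activation in 8.1.8 counts as the first dose, since that decides when the window opens.

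The two End of Study Visit rules (5.3 and footnote 1 of 8.2) should also be reconciled, although the split is needed under either.

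The cost is plan wording and a little programming, with no new data. With at most 25 subjects some cells will be small and their intervals wide.

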9.3.2 Serious Adverse Event Reporting

All SAEs must be reported to Capnia within 24 hours of first knowledge of the event. All SAEs that occur from the time the subject is enrolled through the End of Study Visit are reportable within 24 hours.

The procedure for reporting an SAE is as follows:

- Within 24 hours of first knowledge of the event, the site must contact Capnia by telephone or facsimile to report the event.
- The initial report should include all information known at the time of the report (additional information can be reported as discovered). Initial reporting should not be delayed in order to obtain resolution or follow-up information.
- The site will fax an SAE report, or similar form, that includes the following information, as available:
 - Subject ID
 - Basic demographic information (age, gender, weight)

Protocol 15-001CA
Nasal CO₂

- Relationship to investigational product (drug, device or both)
- The outcomes attributed to the event (death, life-threatening, hospitalization [new or prolonged], disability, congenital anomaly, required medical intervention to prevent permanent impairment/damage, etc.)
- The onset date and severity of the event
- A brief description of the event including frequency and severity of symptoms leading to diagnosis
- A list of relevant test results and lab data
- Any other relevant history
- Date of investigational product administration
- Whether the investigational product was discontinued prematurely
- Investigator's assessment of causality

The completed SAE report should be faxed as soon as possible (within 24 hours) to:

CAPNIA, Inc.
Attn: [name]
[name]
[name]
(+1) [contact] ext. 19 Telephone
(+1) [contact] Mobile
(+1) [contact] Fax

[name] or another representative of Capnia may contact the Investigator to request additional information regarding the event or to confirm information. All SAEs will be entered on the AE eCRF. The same nomenclature should be used on both the SAE report and the AE CRF.

The Investigator is responsible for the complete and timely reporting of all SAEs to Capnia, following up on resolution of the SAE, and expeditiously and simultaneously notifying the responsible IRB of the occurrence and details of the event according to institutional standard procedures. In the event there is a question as to whether the experience is serious, the event should be reported.

9.4 Adverse Event Follow-up

All AEs that are deemed by the Investigator to be related to study drug and/or study device will be followed until resolution or stabilization of the event.

10.0 STATISTICAL METHODS AND ANALYSIS

10.1 General Considerations

Tests will be conducted with a two-sided alpha = 0.05. Descriptive statistics and 95% confidence intervals will be presented with all analyses.

One interim analyses will be performed after 12 subjects have completed the study. All efficacy and safety analyses will be performed at the conclusion of the study.

10.2 Handling of Dropouts or Missing Data

Efficacy analyses (primary and key secondary endpoints) may be performed using the last value carried forward (LVCF) method.

LVCF will be used only for pain scores up to the specified time point that occurred after the first headache treated with the study drug. All other analysis will be performed on observed values. The following rules will be applied for LVCF method for pain scores:

- If there is only baseline headache pain score available prior to rescue or prior to missing headache pain score, the baseline value will be carried forward as the LVCF.

10.3 Endpoints

10.3.1 Primary Efficacy Endpoint

Greatest change from pre-treatment headache pain intensity to post treatment at any time point within 30 minutes of Nasal CO₂ administration.

10.3.2 Method and Timing of Assessing Efficacy

Since this is an open-label, pilot study, all efficacy analyses will be performed after 12 subjects have treated at least 1 cluster attack.

10.3.3 Secondary Efficacy Endpoints

The key secondary endpoints are:

Protocol 15-001CA
Nasal CO₂

- Percentage of subjects experiencing headache pain freedom at 5-60 minutes within the treated attack
- Percentage of subjects with headache relief at 5-60 minutes within the treated attack
- Rescue medication usage
- Subject satisfaction
- Cluster recurrence

This analysis will be assessed for the first headache treated with the investigational product.

10.3.4 Exploratory Efficacy Endpoints

Exploratory efficacy endpoints will be assessed for the first headache and for all headaches.

Exploratory efficacy endpoints include:

- Number of doses per attack
- Consistency of response with repeated treated attacks

All primary, secondary, and exploratory efficacy endpoints will be analyzed for the all headaches analyses as well.

The endpoint for extent of exposure will be the number of doses per subject per headache.

10.3.5 Safety Endpoint

The safety endpoints are adverse events and concomitant medications. Additional safety assessments will include changes from baseline in nasal mucosa.

10.4 Analysis Sets

10.4.1 Intent-to-Treat (ITT) Population

The Intent-to-Treat (ITT) population will consist of all subjects enrolled in the study. The ITT population will primarily be used to describe subject disposition and baseline characteristics.

10.4.2 Modified Intent-to-Treat (mITT) Population

The modified intent to treat (mITT) population will consist of all ITT subjects who treated a headache, received at least one dose of the study drug, and had at least one post treatment efficacy evaluation. The mITT population will be used to conduct all efficacy analyses.

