3.3.3 Clinical Evaluation in Healthy Volunteers

Study C011 was a randomized, double-blind, placebo-controlled study in healthy human volunteers designed to assess the tolerability of nasal CO₂ at different flow rates (0.22 L/min and 0.44 L/min) and using different nosepieces (direct versus indirect flow). Twenty-three subjects

were assigned to receive combinations of high or low flow rate (and placebo) with each type of nosepiece.

In C011, the most common AEs reported were related to the administration site (described in different terms such as nasal discomfort, tingling, burning, pain, stinging, irritation, etc.), lacrimation, rhinalgia, ear/nose/throat discomfort or pain, unusual/unpleasant taste, headache, and rhinorrhea. Additional AEs reported were dizziness/lightheadedness, post-nasal drip, nasal congestion, pressure at forehead or sinus, local hypothesia, left-side facial pain, numbness in throat, wheezy cough, and hot flashes. In general, subjects were able to tolerate the nasal CO₂ administrations, with approximately 90% of administrations being completed. The higher flow rate and direct flow nosepiece were not as well-tolerated as the lower flow rate and diffuse flow nosepieces.

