6.3 Subject Withdrawal

Subjects are free to withdraw consent and discontinue participation in the study at any time without prejudice to further treatment. A subject's participation in the study may be discontinued at any time at the discretion of the Investigator. Justifiable reasons for the removal of a subject from the study include but are not limited to:

- The subject's request
- The subject is non-compliant in the opinion of the Investigator
- The subject resumes or initiates other medication not permitted in this study
- The subject experiences an adverse event which, regardless of seriousness or severity, prohibits further participation in the study
- The subject does not have a cluster headache episode within 84 days (12 weeks) after Enrollment
- The subject becomes pregnant, at which time she is to inform the study site personnel

Enrolled subjects who withdraw from the study must return to the study site for the End of Study Visit. If during this visit, the Investigator determines that the subject has an ongoing study drug-related or study device-related adverse event, the subject will be followed until resolution or stabilization.

The reasons for withdrawal must be documented accordingly in the subject's eSource documents/eCRF. Subjects who withdraw early from the study may be replaced.

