10.4.3 Per Protocol (PP) Population

The per protocol (PP) population is defined as all mITT subjects who had no major protocol violations. Subjects will be analyzed based on the treatment that they actually received. The PP population will be used to analyze the primary and key secondary efficacy endpoints.

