10.4.4 Safety Analysis Set

The safety analysis set will consist of all subjects enrolled in the study who receive at least one administration of investigational product. The safety population will be used for all safety analyses.

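### A subject who treats an attack but leaves no efficacy record is outside every planned efficacy analysis, which in this single-arm trial can only flatter the result if such subjects are failures

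*Combined protocol and SAP*

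**What the plan says.** Section 10.4.2 admits to mITT those enrolled subjects who treated a headache, "received at least one dose of the study drug, and had at least one post treatment efficacy evaluation". It then states: "The mITT population will be used to conduct all efficacy analyses". Section 10.4.3 adds no wider set: "The per protocol (PP) population is defined as all mITT subjects who had no major protocol violations". Section 10.4.1 reserves ITT mainly for disposition and baseline description.

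Four other places bear on who gets in:

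- Section 5.2.1 defines a dose: "One dose will consist of a 10 second administration of nasal CO₂ to each nostril". No section says how an incomplete dose counts.
- Section 10.2 permits, but does not require, last-value-carried-forward for pain scores. Where only a baseline score exists, "the baseline value will be carried forward as the LVCF". Section 10.10 says that the primary analysis leaves missing values unadjusted.
- Section 6.3 lists an adverse event among the reasons for withdrawal and adds: "Subjects who withdraw early from the study may be replaced". It does not separate subjects who have used CO₂ from those who have not.
- Section 10.4.4 sets a looser entry test for safety, namely enrolled subjects "who receive at least one administration of investigational product".

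**The concern.** Entry to the efficacy set depends on something that happens after treatment starts, and tolerability or lack of benefit may influence it. Nasal discomfort is an anticipated effect (Section 3.4). A subject who stops for that reason and records nothing leaves the denominator of the primary change score and of the pain-freedom and relief percentages.

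In a randomised trial, comparable losses in a control arm might expose or partly offset this. Here there is one open-label arm, so the efficacy estimate has no such check. Sections 5.4 and 10.9 also allow the trial to be modified or stopped on signs of efficacy or their absence, so the same denominator could feed those decisions.

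**Working it through.** **Tracing a treated subject through the rules**

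1. *Complete first dose, no efficacy record of any kind.* This subject fails the second condition of Section 10.4.2, so is outside mITT and therefore outside PP. The baseline rule in Section 10.2 would give zero change, but it acts on subjects already in the analysis set and cannot bring this one back.
2. *Only dose aborted before both nostrils are done.* Read literally with Section 5.2.1, this is less than one dose and the subject is out. The document does not confirm that reading.
3. *No pain score in the first 30 minutes, but a one-hour score or a rescue record.* This subject can be in mITT. The primary value then depends on whether Section 10.2 (carry baseline forward, optional) or Section 10.10 (no adjustment) governs.
4. *Subject 1 or 2 then withdraws.* Section 6.3 allows a replacement.

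**Size**

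The plan gives no expected dropout, effect size or SD, so there is no planned figure to reproduce. Inputs:

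- Treated subjects: 25 (Section 5.0).
- Share *q* of treated subjects outside mITT: not given, so assumed. The range runs from 2% to 10%. The top value of 19% is built from Section 3.3.3, which reports "approximately 90% of administrations being completed" in healthy volunteers. Two administrations per dose failing independently give 1 − 0.9² = 0.19.
- Excluded subjects are assumed to be failures with zero change.

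Formulas: expected number excluded = 25*q*; chance of at least one = 1 − (1 − *q*)²⁵; inflation of a response rate or mean change = 1/(1 − *q*).

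| *q* | Expected of 25 | P(at least one) | Inflation |
|---|---|---|---|
| 2% | 0.5 | 0.40 | 1.02 |
| 5% | 1.25 | 0.72 | 1.05 |
| 10% | 2.5 | 0.93 | 1.11 |
| 19% | 4.75 | 0.995 | 1.23 |

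In whole subjects, take 10 responders among 25 treated, with *k* excluded (Clopper-Pearson 95% limits):

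- All 25 kept: 10/25 = 40.0% (21.1 to 61.3)
- *k* = 1: 10/24 = 41.7% (22.1 to 63.4)
- *k* = 3: 10/22 = 45.5% (24.4 to 67.8)
- *k* = 5: 10/20 = 50.0% (27.2 to 72.8)

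For the primary endpoint, an mITT mean change of 1.0 point becomes 1.0 × (25 − *k*)/25 = 0.96, 0.88 and 0.80 for *k* = 1, 3 and 5. If the *k* subjects are replaced so that 25 are evaluable, it becomes 1.0 × 25/(25 + *k*) = 0.96, 0.89 and 0.83.

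**The case against.** Requiring a post-treatment evaluation is a common mITT choice, and this is a small pilot with wide intervals. Several stronger readings are tempting, and the documents do not support them.

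- *That early failures in general drop out.* They do not. Section 8.1.9 asks for scores from 5 minutes on and for a diary during or straight after the headache. Section 7.2.3 asks rescue users to record severity at one hour. Rescue use and satisfaction are listed efficacy endpoints (Section 10.3.3), so a record of either could qualify a subject. Only failure with no record at all is lost.
- *That an aborted first dose is certainly excluded.* This is a literal reading only. Section 8.1.10 has subjects record how long each administration lasted, which suggests that shortened doses might count. A subject may also enter mITT through a second or third attack.
- *That the safety and efficacy sets differ in exactly these subjects.* Training includes using the activated device for 5 seconds per nostril (Section 8.1.8). A subject who never treats an attack could therefore meet the safety definition. Section 10.8 goes further and refers to all enrolled subjects.
- *That aborting a dose or missing a score triggers replacement.* Section 6.3 requires withdrawal, and replacement does not itself remove a withdrawn subject who has data.
- *That the loss would be invisible.* Disposition, withdrawal reasons and adverse events are all reported. What is missing is an efficacy estimate that includes these subjects.
- *That 10% to 19% is the expected loss.* Section 3.3.3 does not say whether an administration means one nostril or two, and its figure comes from healthy volunteers at other flow rates, with placebo included. Elsewhere losses look small: in C213, at 0.5 SLPM, all 20 subjects completed all four treatments (Section 3.3.5.3), and C112 had no discontinuations for adverse events (Section 3.3.4.4).

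These points limit the size of the problem and the confidence in the partial-dose route. They do not restore a treated subject without an efficacy record to any planned efficacy analysis.

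**Conclusion.** The point holds in a limited form. The only efficacy sets are conditional on a post-treatment record, so a treated subject without one is lost from every planned efficacy analysis, and the baseline rule in Section 10.2 cannot help. Whether a partial dose has the same effect is undefined. The direction is favourable to the product if the lost subjects are failures.

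The size rests on an assumed exclusion rate. At 2% to 10% of 25 treated subjects the inflation factor is about 1.02 to 1.11. The value of 1.23 at 19% is the upper end; it assumes independent single-nostril failures, with every such subject both excluded and at zero change. These shifts are small beside the width of the confidence intervals, but they are systematic and cheap to remove. The change should be made; it does not put the trial in question.

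**What to change.** 1. In Section 10.4.2, define the primary efficacy set as every subject who starts any CO₂ administration to treat an attack, complete or not, excluding training use. This also settles how a partial dose counts for analysis.
2. Count a subject with no pain score in the endpoint window as zero change and a non-responder. Section 10.2 cannot simply be cited for this, because its rule is optional and Section 10.10 says the opposite for the primary analysis. Reconcile the two sections so that the rule applies to the primary analysis, and keep the current mITT analysis as a sensitivity analysis.
3. In Section 6.3, state that replacing a subject who has treated an attack does not remove that subject from the efficacy set. Report the number replaced and the reasons.
4. Report how many treated subjects had an incomplete first dose or no post-dose score. Section 8.1.10 already collects the duration of each administration.

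The cost is wording in Sections 10.4.2, 10.2, 10.10 and 6.3 and a few added counts, with no new visits or data collection. The downside is that the reported response may be slightly less favourable.
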